4.4. Treatments

4.4.1. Treatments Administered

5% Monolaurin Vaginal Gel

Monolaurin Vaginal Gel is a clear and colorless non-sterile glycol-based gel for vaginal administration. Monolaurin Vaginal Gel is comprised of 5% monolaurin and the following excipients:

Active test article is comprised of 5% monolaurin prepared as pre-filled vaginal gel applicators of identical likeness to placebo. The components of the applicator are biocompatible and latex-free.

Vehicle Placebo Gel

The Vehicle Placebo Gel is a clear to opaque, colorless to light gray, non-sterile glycol-based gel for vaginal administration and contains the following:

. The Vehicle Placebo Gel contains the same excipients as the active product.

The Vehicle Placebo Gel is comprised of the identical vehicle contained in the active test article prepared as pre-filled vaginal gel applicators of identical likeness to active test article. The components of the applicator are biocompatible and latex-free.

The first dose of Monolaurin Vaginal Gel or Vehicle Placebo Gel is administered by the subject while the subject is still in clinic. The remaining 5 doses are administered twice daily (morning and evening), with at least 8 hours between doses by the subject at home. If the subject receives her first dose after 3 p.m., she is instructed to administer the next dose the following morning.

4.4.2. Method of Assigning Subjects to Treatment Groups (Randomization)

Enrollment of subjects is done online using the enrollment module of AdvantageEDCSM. Subjects are randomly assigned to active drug or placebo in a 2:1 ratio. The study uses a stratified, permuted blocked randomization scheme. Permuted block randomization is used to avoid the potential for serious imbalance in the number of subjects assigned to each group during the study, an imbalance that can occur in the simple randomization procedures. Stratification is by clinical site.

The randomization is prepared by statisticians at the Statistical and Data Coordinating Center (SDCC) and included in the enrollment module for the trial. AdvantageEDC assigns each subject to a treatment group after the demographic and eligibility data have been entered into the system.

The vaginal gel applicators are packaged as a kit sufficient for twice daily administration for 3 consecutive days (six applicators). Random kit numbers are provided to Fisher, the investigational product distributor, in order to ensure the associated sets of applicators are filled with the same contents (placebo or active) without unblinding the sites to what treatment is in

each kit once the shipments arrive. Each vaginal gel dispensing kit is individually labeled with the kit number. Once a subject is assigned a randomization number, a kit corresponding to the assigned treatment is distributed to the subject.

4.4.3. Blinding

A designated individual at each site is provided with a treatment key, which links the treatment code to the actual treatment assignment, which is kept in a secure place.

The applicators of vaginal gels are selected by the unmasked Site Research Pharmacist or designated unmasked study personnel and are distributed to masked study personnel with no labels that identify the product or applicators to the site as Monolaurin Vaginal Gel or Vehicle Placebo Gel.

The volunteers, the study personnel who perform study assessments after administration, data entry personnel at the sites, and laboratory personnel are masked to treatment assignment. The DSMB may receive data in aggregate and presented by treatment group. The DSMB may be unmasked to individual study treatment assignments, as needed, to adequately assess safety issues.

For the interim analysis, the blind was maintained when reporting results prepared for the DSMB meeting.

4.5. Efficacy and Safety Variables

Subject assessment of solicited urogenital adverse events constitutes a primary safety endpoint. Solicited event assessments were captured on a memory aid starting on Day 1, the first day of therapy and continuing for 5 days. The subject was to record the presence and intensity of vulvovaginal solicited events on the memory aid. Any symptom that was present at the time that the subject was screened should have been considered as baseline and not reported as a solicited urogenital AE. However, if the symptom deteriorated at any time during the study, it was to be recorded as an AE. If a symptom was reported that was not present at baseline, it too was to be recorded as an AE. Any symptoms still present on Day 5 were continued to be followed by subject memory aid notations until symptom resolution. Solicited events include vaginal odor, vaginal pain, vaginal tenderness, vulvar/vaginal itching, vaginal dryness, vaginal discharge, and vulvar inflammation. Severity of solicited events symptoms are graded according to the table in Appendix C in the protocol. Symptoms not specifically mentioned will be graded using the following scale:

- Grade 1: Mild (does not interfere with activity)
- Grade 2: Moderate (interferes with activity)
- Grade 3: Severe (prevents daily activity)

Clinical laboratory evaluations constitute a secondary safety endpoint. Hematology includes: WBC count, hemoglobin, platelets, and neutrophil count. Clinical chemistry includes: creatinine, AST (SGOT), ALT (SGPT), total bilirubin, and glucose (random). Grade 3 abnormal laboratory values were to be repeated within 10 days. Laboratory abnormalities that were stable at Visit 2 were not repeated at Visit 3. Laboratory abnormalities that occurred between Visit 1 and Visit 2 or worsened at Visit 2 were repeated at Visit 3. A laboratory abnormality is considered an adverse event if there was a worsening of the laboratory value at Visit 2 from the baseline value and it increased in laboratory toxicity grading from the baseline toxicity grading. For laboratory abnormalities repeated at Visit 3, if there was a worsening of the laboratory value at Visit 3 from the Visit 2 value and it increased in laboratory toxicity grading, it was considered an additional adverse event.

Multiple observations within a specific visit period are accepted. In the case of multiple observations within a specific window, the assessment value that is closest to the scheduled visit window will be used in the analyses for the post-baseline records. For screening and baseline visits, the last assessment value prior to first dose will be used as the baseline measurement. All the recorded data will be listed. If observations have the same distance to the scheduled assessment, the latest one will be used.

Culture counts for following bacterial and yeast species will be collected: Lactobacillus, Gardnerella, Mobiluncus, and Candida. Nugent score and Budding yeast will be reported from the Gram Stain. Budding yeast will be categorized as Few, Moderate, Many, or No organisms seen.

See Section 3.3 for efficacy variable definitions.

5. SAMPLE SIZE CONSIDERATIONS

The statistical informational goal for the study is 90 subjects eligible for the primary efficacy analysis of clinical cure in the modified Intent-to-Treat (mITT) efficacy population. This is an ad-hoc sample size determined by logistical and feasibility considerations, as there is insufficient pilot data upon which to base more formal sample size calculations.

Subjects who did not meet all inclusion/exclusion criteria, who have a Nugent score <4 at Visit 1 or are positive for other concomitant vulvovaginal infections at baseline which may interfere with the efficacy assessment will be excluded from the mITT population.

Based on observed rates of these outcomes at the participating clinics, it is anticipated that a total of 120 subjects will be enrolled to reach this target. However, enrollment will be continued past 120 subjects to a maximum of 150, if necessary, to reach the informational goal of 90 eligible subjects.

The table below shows the statistical power conferred by this sample size for a two-sided significance level 5% Fisher's exact test comparing binomial proportions, under different assumed proportions.

Power to compare binomial proportions using a two-sided significance level 0.05 Fisher's Exact Test with a sample size of N = 90 (60 subjects in the 5% Monolaurin Vaginal Gel arm, 30 subjects in the Vehicle Placebo Gel arm) is shown below. Conditions in which Power is \geq .80 are highlighted.

	5% Monolaurin Vaginal Gel (N=60)											
		.05	.10	.20	.30	.40	.50	.60	.70	.80	.90	.95
•	.05	.02	.04	.38	.82	.97	>.99	>.99	>.99	>.99	>.99	>.99
(= 3 0	.10	.13	.03	.15	.52	.85	.98	>.99	>.99	>.99	>.99	>.99
el (N	.20	.53	.22	.03	.12	.42	.78	.96	>.99	>.99	>.99	>.99
bo G	.30	.86	.61	.15	.03	.12	.41	.76	.95	>.99	>.99	>.99
lace	.40	.98	.89	.47	.13	.04	.13	.41	.76	.96	>.99	>.99
le P	.50	>.99	.98	.79	.42	.13	.04	.13	.42	.79	.98	>.99
ehic	.60	>.99	>.99	.96	.76	.41	.13	.04	.13	.47	.89	.98
Λ	.70	>.99	>.99	>.99	.95	.76	.41	.12	.03	.15	.61	.86
	.80	>.99	>.99	>.99	>.99	.96	.78	.42	.12	.03	.22	.53
	.90	>.99	>.99	>.99	>.99	>.99	.98	.85	.52	.15	.03	.13
	.95	>.99	>.99	>.99	>.99	>.99	>.99	.97	.82	.38	.04	.02

With respect to the safety objectives, for a sample size of 60 subjects in the treatment arm with no observed SAEs related to study product, the 95% confidence interval (CI) for the estimated proportion is (.00,.06) (Clopper-Pearson interval).

In actuality, the safety analysis cohort will be larger than the mITT cohort, and the CI will be more precise than this.

6. GENERAL STATISTICAL CONSIDERATIONS

6.1. General Principles

Tabulations will be used extensively to summarize the data. All continuous variables will be summarized using the following descriptive statistics: n (sample size), mean, standard deviation, median, maximum and minimum. The frequency and percentages (based on the sample size) of observed levels will be reported for all categorical measures. Wilson confidence intervals for binomial proportions and differences in binomial proportions will be computed for efficacy variables. Clopper-Pearson confidence intervals for binomial proportions and differences in binomial proportions and differences in binomial proportions and differences in binomial proportions will be computed for safety variables. In general, all data will be listed by treatment group and/or subject, and when appropriate by visit number within subject.

All summary tables will be structured with a column/sub-table for each treatment group (5% Monolaurin Vaginal Gel, Placebo Gel, and All Subjects). The total population size relevant to that table/column if applicable, including any missing observations will be displayed in the tables.

Note that in the data listings, Subject ID is the unique subject identifier, not the Study ID used on study and dates will not be included, only Study Day. Study Day 1 will be the day of the first dose of treatment.

6.1.1. Pseudo Code

The following SAS® peudo code will be used to calculate the following:

Fisher's Exact test:

```
proc freq;
Table treatment*analysis_variable / exact;
ods output FishersExact=outputdsn1;
run;
```

95% Wilson CI for proportions/percents:

```
Proc freq;
Table treatment*analysisvariable / binomial(wilson);
    ods output binomialcls=outputdsn2;
Run;
```

95% Wilson CI for difference in proportions (produces Newcombe CI):

```
Proc freq;
Table treatment*analysisvariable / riskdiff(cl=Wilson);
Exact Riskdiff;
ods output pdiffcls=outputdsn3;
Run;
```

95% Clopper-Pearson CI for proportions/percents:

```
Proc freq;
Table treatment*analysisvariable / binomial(clopperpearson);
ods output binomialcls=outputdsn2;
Run;
```

95% Exact CI for difference in proportions:

```
Proc freq;
Table treatment*analysisvariable / riskdiff(cl=Exact);
Exact Riskdiff;
ods output pdiffcls=outputdsn3;
Run;
```

6.2. Timing of Analyses

The fully blinded interim analysis will be performed when 80 subjects have been enrolled and have available baseline test results for Nugent score, HIV, Chlamydia, and gonorrhea.

The final analysis will be performed after database lock when all subjects have been followed through Visit 3, the final study visit, at Day 28 (Window: Days 22-30).

6.3. Analysis Populations

A tabular listing of all subjects, visits, and observations excluded from the efficacy analysis will be provided in the CSR (Listing 4). Five analysis populations will be used in the analyses, the Intent-to-Treat (ITT), Safety, mITT, Evaluable, and Per Protocol (PP). A listing of subjects whose assigned treatment group does not match their randomized treatment group will be provided in Listing 20.

6.3.1. Intent-to-Treat Analysis (ITT) Population

The ITT population includes all randomized subjects, regardless of whether or not they received study treatment. In the unlikely event of an error in randomization or study product administration (i.e., incorrect product), subjects will be grouped by their intended randomized assignment.

6.3.2. Safety Analysis Population

The safety population includes all randomized subjects who received at least one dose of study treatment. In the unlikely event of an error in randomization or study product administration (i.e., incorrect product), subjects will be grouped by the product they actually received.

6.3.3. Modified Intention-to-Treat (mITT) Population

The mITT population includes all randomized subjects who met all inclusion/exclusion criteria, excluding those who have a Nugent score <4 at Visit 1 or a positive Visit 1 HIV, Chlamydia, or Neisseria gonorrhoeae test. A review of medical history and concomitant medications will be performed to identify any other infections that may interfere with the efficacy assessment. Subjects with these identified infections will be excluded from the mITT population. In the unlikely event of an error in randomization or study product administration (i.e., incorrect product), subjects will be grouped by their intended randomized assignment. The mITT population will be used as the primary analysis population for the primary efficacy endpoint test of 5% Monolaurin Vaginal Gel to Vehicle Placebo Gel.

6.3.4. Evaluable Population

The Evaluable population includes all subjects in the mITT population who received study treatment and returned for at least one post-baseline visit that includes an assessment of efficacy.

In the unlikely event of an error in randomization or study product administration (i.e., incorrect product), subjects will be grouped by the product they actually received.

6.3.5. Per Protocol Population

The Per Protocol (PP) population for all endpoints measured at Visit 2 includes all randomized subjects who met all inclusion/exclusion criteria, did not have sexual intercourse including receptive oral sex or insertion of substances or objects intravaginally between Visit 1 and Visit 2, complied with the assigned study treatment, returned to the study site for the Test of Cure visit within the specified window (Visit 2 Study Day 8 relative to the first day of treatment [Window: Days 8-15]), or discontinued study product early due to lack of treatment effect or received vaginosis or systemic antimicrobial therapy other than study drug before Visit 2. Subjects with

Visit 1 test results including a grade 3 laboratory abnormality, a positive Visit 1 HIV, Chlamydia, or *Neisseria gonorrhoeae* test, are found to have a PAP result consistent with HSIL, AGUS, or CIN2 or greater, or a Visit 1 Nugent score < 4 will be excluded from the PP population. A review of medical history and concomitant medications will be performed to identify any other infections that may interfere with the efficacy assessment. Subjects with these identified infections will be excluded from the PP population.

The PP population for all endpoints measured at Visit 3 includes all randomized subjects who met all inclusion/exclusion criteria, did not have sexual intercourse including receptive oral sex or insertion of substances or objects intravaginally between Visit 1 and Visit 2 or 48 hours before Visit 3, complied with the assigned study treatment, returned to the study site for Visit 2 and Visit 3 within the specified windows (Visit 2 Study Day 8 relative to the first day of treatment [Window: Days 8-15]), Visit 3 Study Day 28 relative to the first day of treatment [Window: Days 8-15]), or discontinued study product early due to lack of treatment effect or received vaginosis or systemic antimicrobial therapy other than study drug between Visits 1 and 3. Subjects with Visit 1 test results including a grade 3 laboratory abnormality, a positive Visit 1 HIV, Chlamydia, or Neisseria gonorrhoeae test, are found to have a PAP result consistent with HSIL, AGUS, or CIN2 or greater, or a Visit 1 Nugent score < 4 will be excluded from the PP population. A review of medical history and concomitant medications will be performed to identify any other infections that may interfere with the efficacy assessment. Subjects with these identified infections will be excluded from the PP population.

See Section 9.2 for measurements of compliance.

In the unlikely event of an error in randomization or study product administration (i.e., incorrect product), subjects will be grouped by the product they actually received.

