## 5. STUDY ENROLLMENT AND WITHDRAWAL

# 5.1. Subject Inclusion Criteria

It is the intent of this study to enroll women who are generally healthy with evidence of BV on gynecological evaluation. Subjects may have asymptomatic BV, but must meet any three of the four Amsel criteria for BV as defined in section 7.1. Inclusion criteria must be assessed by a clinician licensed to make medical diagnoses. Subjects must meet all of the following inclusion criteria to participate in this study:

- 1. Non-pregnant, non-breastfeeding females between the ages of 18 and 50 years, inclusive.
- 2. Women of childbearing potential\* must agree to practice reliable contraception\*\* for the 28-day period before enrollment through 30 days following treatment.
  - \*(not surgically sterile via tubal ligation, bilateral oophorectomy or hysterectomy, or who have not been postmenopausal for  $\geq 1$  year)
  - \*\* Acceptable birth control methods for the purposes of this study may include, but are not limited to, abstinence from intercourse with a male partner, monogamous relationship with vasectomized partner, barrier methods to include condoms and diaphragms, intrauterine devices, and licensed hormonal methods. NuvaRing® contraceptive use will be prohibited from this study since the device can alter vaginal secretions.
- 3. Presenting with signs of BV (as per Amsel Criteria). Subjects must meet any three of the four criteria for enrollment\*
  - \*Presence of discharge, greater than or equal to 20% clue cells on wet prep, positive "whiff test" on KOH prep, vaginal pH of greater than 4.5.
- 4. Not currently menstruating or expected to in the next 4 days.
- 5. Able to understand and comply with planned study procedures.
- 6. Willing to abstain from sexual intercourse, insertion of tampons, douches, or other intravaginal medications or objects between Visit 1 and Visit 2 and 48 hours prior to Visit 3.
- 7. Provide written informed consent before initiation of any study procedures and be available for all study visits.
- 8. No known history of HIV.

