## 11.2. Data Analysis Populations

The Per-Protocol (PP) efficacy analysis population includes all randomized subjects who met all inclusion/exclusion criteria, did not have any significant protocol deviations, complied with the assigned study treatment, returned to the study site for the Test of Cure visit within the specified window (Visit 2 Study Day 8 relative to the first day of treatment [Window: Days 8-15]), or discontinued study product early due to lack of treatment effect or received vaginosis or systemic antimicrobial therapy other than study drug during the study. Subjects with Visit 1 test results including a grade 3 laboratory abnormality, a positive Visit 1 HIV, *Chlamydia*, or *Neisseria gonorrhoeae* test, a PAP result consistent with HSIL, AGUS, or CIN2 or greater, or a Visit 1 Nugent score < 4 will excluded from the PP population.

A subject is compliant with study treatment if she uses at least 5 of 6 doses of study product, as assessed by the study coordinator's count of used / unused applicators in each returned subject kit. If a kit is not returned, compliance will be assessed by the subject's self-report on the memory aid. Significant protocol deviations include sexual intercourse including receptive oral sex or insertion of substances or objects intravaginally between Visit 1 and Visit 2.

The Modified Intent-to-Treat (mITT) efficacy analysis population includes all randomized subjects who met all inclusion/exclusion criteria excluding those who have a Nugent score <4 at Visit 1 or are positive for other concomitant vulvovaginal infections at baseline which may interfere with the efficacy assessment. The mITT population will be used as the primary analysis population for the test of 5% Monolaurin Vaginal Gel to Vehicle Placebo Gel.

The Evaluable efficacy analysis population includes all subjects in the mITT population who received study treatment and returned for at least one post-baseline visit.

The Intent-to-Treat (ITT) efficacy analysis population includes all randomized subjects.

The safety population includes all randomized subjects who received at least one dose of study product.

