8.2. Secondary Efficacy Analyses

Secondary efficacy analyses will be performed in the mITT, ITT, Evaluable and PP populations. The mITT and ITT populations will be summarized by randomized treatment and the Evaluable and PP populations will be summarized by actual treatment received.

Table 30 presents the proportion of subjects with clinical cure in each treatment group at Visit 3 (Day 22-31). The number of subjects, the proportion of subjects who achieved clinical cure (clinical cure rate), and the 95% Wilson confidence interval for the proportion of subjects achieving clinical cure will be presented for each analysis population and treatment group. In addition, the difference in proportions between the 5% Monolaurin Vaginal Gel arm and the Placebo gel arm and 95% Wilson confidence intervals will be presented.

Tables 31 and 32 present the proportion of subjects with therapeutic cure in each treatment group at Test of Cure Visit, Visit 2 (Day 8-15) and at Visit 3 (Day 22-31), respectively. The number of subjects, the proportion of subjects who achieved therapeutic cure (therapeutic cure rate), and the 95% Wilson confidence interval for the proportion of subjects achieving therapeutic cure will be presented for each analysis population, treatment group, and study visit. In addition, the difference in proportions between the 5% Monolaurin Vaginal Gel arm and the Placebo gel arm and 95% Wilson confidence intervals will be presented.

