12. SUMMARY OF CHANGES IN THE CONDUCT OF THE STUDY OR PLANNED ANALYSES

Protocol version 5.0 (August 31, 2016) changed the criterion requiring all four Amsel criteria for inclusion to any 3 of 4 Amsel criteria; changed the allowable interval between a previous vaginal/cervical/pelvic infection or episode of BV from 60 days prior to enrollment to 14 days and removed the prohibition of systemic, vaginal or perineal immunosuppressant or antiinflammatory medications within 14 days of treatment; and changed the procedure for review of the Gram stain when two independent reviewers have different Nugent scores. Protocol version 6.0 (November 29, 2016) included the addition of a clinical site, Duke University, and clarification of temperature range for specimen storage. Protocol version 7.0 (May 11, 2017) removed the criterion requiring subjects over age 21 to report a normal PAP smear within the past 3 years, revised the exclusion for HPV and cervical or vaginal dysplasia to exclude only HSIL, AGUS, or CIN2 or higher, changed exclusions for previous self-treatment for yeast vaginitis and systemic, vaginal, or perineal antibiotics from 14 days to 7 days, and removed exclusion for 6 or more episodes of vaginitis within the past year, clarified that subjects found to have HSIL or AGUS at visit 1 will have study treatment discontinued and subjects found to have HSIL, AGUS, or CIN2 or higher at visit 1 will be excluded from the PP analysis population, and corrected protocol deviation plan such that sexual intercourse 48 hours prior to Visit 3 will not exclude subjects from the Per-Protocol data analysis population definition. Protocol version 8.0 (May 23, 2017) removed exclusion for diabetes.

Protocol Section 11.3 states Last Observation Carried Forward (LOCF) will be used as a sensitivity analysis. Section 6.5 of this analysis plan clarifies that LOCF will be used to impute the cure status of subjects whose status cannot be determined at Visit 3 for any reason. Subjects whose status cannot be determined at the TOC visit, will be considered 'not cured' for all cure-related endpoints.

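### The SAP's Visit 3 per-protocol set adds an undeclared exclusion for intercourse or insertion in the 48 hours before Visit 3, which Protocol 11.2 does not contain and which SAP Section 12 says was dropped for intercourse

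*SAP*

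**What the plan says.** Protocol 11.2 defines one PP population, built around the Test of Cure visit (Visit 2). The behavioural breach it names is limited to the first interval: "Significant protocol deviations include sexual intercourse including receptive oral sex or insertion of substances or objects intravaginally between Visit 1 and Visit 2".

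SAP 6.3.5 splits PP by visit. For Visit 2 endpoints its criterion agrees with the protocol: no intercourse or "insertion of substances or objects intravaginally between Visit 1 and Visit 2, complied with the assigned study treatment". For Visit 3 endpoints it adds a second interval, covering "objects intravaginally between Visit 1 and Visit 2 or 48 hours before Visit 3, complied with the assigned study treatment".

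SAP Section 12, describing protocol version 7.0, says the deviation plan was corrected so that "sexual intercourse 48 hours prior to Visit 3 will not exclude subjects from the Per-Protocol data analysis population definition".

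Section 12 also records where the SAP itself departs from the protocol. It does so for missing data ("Protocol Section 11.3 states Last Observation Carried Forward (LOCF) will be used as a sensitivity analysis", followed by the SAP's different use), and SAP 6.5 flags the same change. It records nothing for the Visit 3 PP criterion.

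The abstinence request itself remains in the current protocol. Inclusion criterion 6 in Protocol 5.1 asks for willingness to abstain from intercourse, tampons, douches "or other intravaginal medications or objects between Visit 1 and Visit 2 and 48 hours prior to Visit 3".

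**The concern.** A programmer who follows SAP 6.3.5 will drop from the Visit 3 PP tables some women whom Protocol 11.2 does not exclude. For intercourse, the SAP's own Section 12 says they should not be dropped. The two documents, and two sections of the SAP, therefore give different membership rules for the same analysis set.

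The set is used. SAP 8.2 states: "Secondary efficacy analyses will be performed in the mITT, ITT, Evaluable and PP populations". SAP 8.3 says the same of the exploratory analyses. Visit 3 clinical cure, therapeutic cure and Nugent category, the first-time and recurrent BV subgroups, and the culture counts all have PP versions.

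Behaviour in the two days before Visit 3 comes about four weeks after randomisation. It could plausibly be related to whether symptoms have cleared. If it is, excluding on it selects partly on the outcome. A membership rule that is still ambiguous at unblinding also leaves room for the choice to look result-driven.

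**Working it through.** No figure in the plan bears on this point. The check is a comparison of text, followed by an illustration under stated assumptions.

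**Text comparison**

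| Source | Visit 1 to Visit 2 | 48 hours before Visit 3: intercourse | 48 hours before Visit 3: insertion |
|---|---|---|---|
| Protocol 11.2 (PP) | excludes | not listed | not listed |
| SAP 6.3.5, Visit 2 PP | excludes | not listed | not listed |
| SAP 6.3.5, Visit 3 PP | excludes | excludes | excludes |
| SAP Section 12, on version 7.0 | not discussed | expressly does not exclude | not mentioned |
| Protocol 5.1, criterion 6 (conduct) | abstain | abstain | abstain |

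1. The third row differs from the first in both 48-hour columns. That difference does not depend on Section 12.
2. The third and fourth rows conflict directly for intercourse. Section 12 is a record of changes, but the state it attributes to version 7.0 is the state of the current version 8.0 text in Protocol 11.2. The only version 8.0 change Section 12 reports is removal of the diabetes exclusion. The conflict is therefore not with superseded wording.
3. For insertion, the only support is absence from Protocol 11.2.
4. The last row is an instruction on conduct. Protocol 11.2 does not carry its Visit 3 part into PP membership.

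**Illustration of sensitivity**

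Assume a Visit 3 PP set of 60 and 30 women before the 48-hour rule. These are the mITT planning numbers, so a real PP set would be smaller. Assume cure in 30/60 and 6/30. The difference is 0.50 − 0.20 = 0.30, with Newcombe 95% CI 0.09 to 0.46 (the interval type in SAP 6.1.1).

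Suppose about 5% are excluded (3 active, 2 placebo, leaving 57 and 28):
- All excluded active women cured, no excluded placebo woman cured: 27/57 − 6/28 = 0.474 − 0.214 = 0.26.
- The reverse: 30/57 − 4/28 = 0.526 − 0.143 = 0.38.

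Suppose 10% are excluded (6 active, 3 placebo, leaving 54 and 27):
- All excluded active women cured, no excluded placebo woman cured: 24/54 − 6/27 = 0.444 − 0.222 = 0.22 (CI −0.00 to 0.40).
- The reverse: 30/54 − 3/27 = 0.556 − 0.111 = 0.44 (CI 0.23 to 0.59).
- Only uncured women excluded in both arms: 30/54 − 6/27 = 0.33. Only cured women excluded in both arms: 24/54 − 3/27 = 0.33.

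A milder pattern: assume true cure of 40% and 20%, with 25% of cured and 10% of uncured women dropped in each arm.
- Active: 0.40 × 0.75 = 0.30 cured and 0.60 × 0.90 = 0.54 uncured kept, so 0.30/0.84 = 35.7%.
- Placebo: 0.20 × 0.75 = 0.15 and 0.80 × 0.90 = 0.72, so 0.15/0.87 = 17.2%.
- The difference is 18.5 points instead of 20. The odds ratio is unchanged: (0.40/0.60)/(0.20/0.80) = 2.67 and (0.30/0.54)/(0.15/0.72) = 2.67.

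The estimate can move up, down or very little, depending on exclusion rates that the documents do not give. The 5% and 10% cases with opposite patterns in the two arms are extreme bounds, not predictions.

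**The case against.** The best defence is that the rule is a deliberate, visit-specific refinement. Protocol 11.2's single PP set is centred on Visit 2, and under one set a breach before Visit 3 would also have removed a woman from the Visit 2 analysis. Version 7.0 prevents that, and the Visit 2 PP definition in SAP 6.3.5 respects it. The SAP then builds a separate Visit 3 set, and the notes to Listing 4 require the visit to be specified for PP exclusions. Women are still asked to abstain for 48 hours, compliance is reviewed at Visit 3, and Protocol 11.7 leaves analysis detail to the SAP. Protocol 11.2 introduces its behavioural deviations with an open verb, so the list is not strictly closed. There is also a measurement argument: Protocol 2.1 says the abnormal discharge occurs especially after sex, and discharge is one of the Amsel criteria that decide cure.

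Much of this stands. A visit-specific PP set is a reasonable design, so a reader who infers that the Visit 3 PP results would come from the wrong women goes further than the documents allow. They show only that the set differs from the protocol's. A reader might also infer that Section 12 removed the whole criterion, but it names intercourse only. Nor can it be inferred that the rule biases the comparison in a known direction. PP already conditions on post-randomisation behaviour through treatment compliance and the Visit 1 to Visit 2 criterion, and deleting the clause does not remove that selection.

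The defence does not explain the silence. The SAP flags its missing-data departure twice and this one nowhere. The only thing Section 12 says about the 48-hour window points the other way.

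**Conclusion.** The point holds as an undeclared and unreconciled difference. SAP 6.3.5 applies a Visit 3 PP exclusion that Protocol 11.2 lacks. For intercourse it contradicts SAP Section 12. For insertion it goes beyond Protocol 11.2 without any express statement that the criterion had been removed.

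The reach is limited to the PP versions of the Visit 3 secondary and exploratory estimates. The primary efficacy comparison is at Visit 2, and Protocol 11.2 states: "The mITT population will be used as the primary analysis population for the test of 5% Monolaurin Vaginal Gel to Vehicle Placebo Gel". Neither that analysis nor the Visit 2 PP analysis changes. Visit 3 cure is also reported in the mITT, ITT and Evaluable populations. No efficacy test is planned at Visit 3: SAP 8.2 gives proportions, differences and confidence intervals, and the Table 30 shell has no p-value column. Listings 4 and 8 would let a reader trace the exclusions afterwards.

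The size and direction of any effect cannot be determined from the documents. The figures in the illustration rest wholly on assumed cure and exclusion rates, and the conclusion does not depend on them.

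**What to change.** Before unblinding, delete the clause on the 48 hours before Visit 3 from the Visit 3 PP definition in SAP 6.3.5. Its behavioural criterion then matches Protocol 11.2 (Visit 1 to Visit 2 only) and Section 12. If the influence of recent intercourse or insertion is of interest, show the 48-hour restriction as a labelled sensitivity analysis. Listing 8 already captures the data.

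If the sponsor does intend a visit-specific criterion, it should keep the clause, declare and justify it in Section 12 as a departure from Protocol 11.2 (covering intercourse and insertion separately), and also report Visit 3 results in the protocol-defined PP set.

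The same sentence needs editing anyway. It gives the Visit 3 window as Days 8-15, where the protocol and the rest of the SAP's endpoint definitions have Days 22-31. That is a separate slip.

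The first option costs one phrase. Its downside is that some women with recent intercourse or insertion stay in the Visit 3 PP set, as the protocol already provides. The second option costs a short justification and one extra set of Visit 3 PP estimates.
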